12.1. Adverse Events

This study will use CTCAE, version 5.0, for AE reporting. The highest CTCAE grading per cycle and per subject will be computed.

All treatment-emergent adverse events (TEAEs) will be coded using the MedDRA version 21.0 or higher. System organ class, high-level group term (HLGT), high-level term (HLT), preferred term (PT), and lowest level term (LLT) will be provided.

For all other TEAEs not described in the CTCAE criteria, the intensity will be assessed by the investigator as mild (Grade 1), moderate (Grade 2), severe (Grade 3), life-threatening (Grade 4), or death (Grade 5). TEAE with missing grade will be reported under the category “Missing”.

12.1.1. Treatment-emergent adverse events (TEAEs)

Adverse events will be analyzed in terms of TEAEs which are defined as AEs occurring or worsening on or after the date of start of treatment and within 30 days after the last treatment administration. AEs present at baseline which resolve during treatment and occurred again (at any grade) are considered TEAEs. AEs present at baseline which did not resolve within 30 days of the last treatment or which resolved but did not occur again are excluded from TEAEs.

Unless otherwise specified, summary of TEAEs will be provided for the whole study time and per period, overall and per treatment arm.

An overall summary of TEAEs will be provided for:

- subjects with at least one TEAE;
- subjects with at least one TEAE related to any study drug;
- subjects with at least one treatment-emergent serious AE (SAE)
- subjects with at least one treatment-emergent serious AE (SAE) related to any study drug;
- subjects with at least one CTCAE Grade 3 or 4 TEAE;
- subjects with at least one CTCAE Grade 3 or 4 TEAE related to any study drug;
- subjects with at least one TEAE leading to death (Grade 5);
- subjects with at least one TEAE leading to death (Grade 5) related to any study drug;
- subjects with at least one TEAE leading to dose reduction;
- subjects with at least one TEAE leading to dose interruption;
- subjects with at least one TEAE leading to study drug withdrawal;

In addition, TEAEs will be summarized per SOC and per PT for the following:

- all TEAEs;
- TEAEs, occurring for more than 10% of subjects in any treatment group;
- TEAEs related to any study drug (TMZ, MRZ);
- CTCAE Grade 3 or 4 TEAE;
- CTCAE Grade 3 or 4 TEAE related to any study drug;
- TEAEs by age group, for the whole study time only;
- TEAEs by sex, for the whole study time only;
- TEAEs by race, for the whole study time only;
- Treatment-emergent serious AEs (SAEs);
- Treatment-emergent serious AEs (SAEs) related to any study drug;
- TEAEs leading to death;
- TEAEs related to any study drug leading to death;
- TEAEs leading to dose reduction;
- TEAEs leading to dose interruption;
- TEAEs leading to study drug withdrawal.

Subjects with multiple occurrences of the same event will be counted only once per subject for each summary. Results will be reported in descending order of overall subject frequency in the overall column (unless otherwise specified) by SOC and by PT within the SOC. For summaries

by severity grade, the highest grade out of the same TEAEs underwent by a subject will be reported.

Listings for the corresponding summary tables will be presented separately.

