#### SAEs and Related SAEs

After reconciliation with the SAEs listing extracted from the EORTC pharmacovigilance database, the worst grade of each (related) serious AE category will be calculated for each patient. Tables with all grades, grades 3/4 and grades 5 frequencies and percentages in each (related) SAE term will be displayed.

In a separate table, the frequencies and percentages of patients with at least one grade ( $\geq 1$ ) or one grade 3/4 or one grade 5 (related) SAE of any event will be presented.

All deaths, as well as deaths within 30 days after last dose of study treatment, will be tabulated.

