## 16.6 Reporting procedure for investigators

This procedure applies to all Serious Adverse Events (SAEs) occurring from the time a subject is randomized until 30 days after last protocol treatment *administration* and to any SAE that occurs outside of the SAE detection period (after the 30-days period), if it is considered to have a reasonable possibility to be related to the protocol treatment or study participation.

|  |                   |
|--|-------------------|
| Randomization till 30 days after last protocol treatment administration : | All SAEs          |
| From day 31 after last protocol treatment administration :                | Only related SAEs |

Any secondary malignancy should also be reported in expedited way as an SAE with the appropriate seriousness criteria!

All reporting must be done by the principal investigator or authorized staff member (i.e. on the signature list) to confirm the accuracy of the report.

All SAEs must be reported immediately and no later than 24 hours from the time the investigator or staff became aware of the event.

All SAE-related information needs to be provided in English.

If any relevant additional document in local language is uploaded or forwarded to the Pharmacovigilance Unit relevant to an SAE (e.g. autopsy report), this must be accompanied by a translation in English, or the relevant information must be summarized in the electronic SAE-form.

Investigators participating through EORTC must report all SAE-related information to the Medidata Rave EDC system ([www.imedidata.com](http://www.imedidata.com)).

If the iMedidata Rave EDC system is out of service, contact the Pharmacovigilance Unit for further instructions to report your SAE/Pregnancy:

EORTC Pharmacovigilance Unit:

Email: [[contact]](mailto:[contact])

[contact]

[contact]

Investigators participating through non-EORTC groups should consult their group specific appendix for further details on the reporting of Serious Adverse Events.

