11.5. Subgroup Analyses

Overall survival and PFS will also be analyzed within the following subgroups:

- MGMT
- Age (≤ 55 , >55 years),

- Sex (male, female),
- Karnofsky performance status (70/80, 90/100),
- MMSE (≤ 27 , > 27),
- Baseline steroid use (yes, no),
- Extent of surgery (partial/biopsy, gross total).

Additional subgroup analyses based on other baseline disease characteristics might be performed as appropriate.

12. Safety Analysis

All safety analyses will be conducted using the SP.

The safety and tolerability will be followed from study treatment initiation through up to 30 days after the last administration of study treatment. The safety analyses will be reported for the whole study time and by treatment period for the safety analysis as defined below:

The concomitant period (TMZ/RT or TMZ/RT+MRZ) will start on the day of the first administration of radiation therapy and end 27 days after the day of the last administration of radiation therapy and before the start of adjuvant TMZ period whichever occurred first.

The adjuvant TMZ period (ie, when TMZ is administered alone or with MRZ) will start on the day of the first dose of adjuvant TMZ and end up to 27 days after the first day of administration of the last cycle of adjuvant TMZ

The maintenance MRZ period (ie, when MRZ is administered alone after discontinuation of TMZ) will start 28 days after the first day of administration of the last cycle of adjuvant TMZ and end up to 27 days after the first day of administration of the last cycle of maintenance MRZ.

The follow-up period (ie, when all treatments are discontinued) will start 28 days after the first day of administration of the last cycle of maintenance MRZ or adjuvant TMZ up to 30 days after the last treatment administration (MRZ or TMZ)

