12.1.2. Deaths

All deaths, as well as deaths within 30 days after last dose of study treatment, will be tabulated.

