12.1.3. Adverse Events of Special Interest

BMS provided EORTC with a list of adverse events of special interest (AESIs). The categories for AESIs are as followed which are defined by MedDRA SMQs, HLTs, and PTs

- 1) Ataxia including Fall, Gait Disturbances, and Balance Disorders/Dizziness
- 2) Dysarthria
- 3) Hallucination/Delirium

Unless otherwise specified, summaries of treatment-emergent AESIs will be provided for the whole study time and per period, overall and per treatment arm.

Overall summaries of AESIs will be provided for:

- subjects with at least one AESI;
- subjects with at least one AESI related to any study drug;
- subjects with at least one serious AESI (SAE);
- subjects with at least one serious AESI (SAE) related to any study drug;
- subjects with at least one CTCAE Grade 3 or 4 AESI;
- subjects with at least one CTCAE Grade 3 or 4 AESI related to any study drug;
- subjects with at least one AESI leading to death;
- subjects with at least one AESI related to any study drug leading to death;
- subjects with at least one AESI leading to dose reduction,
- subjects with at least one AESI leading to dose interruption
- subjects with at least one AESI leading to study drug withdrawal;

In addition, treatment-emergent AESIs will be summarized per AESI category and per PT for the followings:

- all AESIs;
- AESIs related to any study drug;
- CTCAE Grade 3 or 4 AESIs;

- CTCAE Grade 3 or 4 AESIs related to any study drug;
- AESIs by age group , for the whole study and overall;
- AESIs by sex, for the whole study and overall;
- AESIs by race, for the whole study and overall;
- Serious AESIs (SAEs);
- Serious AESIs (SAEs) related to any study drug;
- AESIs leading to death;
- AESIs leading to death related to any study drug;
- AESIs leading to dose reduction;
- AESIs leading to dose interruption;
- AESIs leading to study drug withdrawal.

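### Related SAEs and secondary malignancies collected from day 31 after last treatment enter no AE table or listing specified in SAP 12.1

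*SAP*

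**What the plan says.** **Collection.** Protocol 16.6 requires all SAEs from randomization to 30 days after the last protocol treatment. After that it still requires "any SAE that occurs outside of the SAE detection period (after the 30-days period), if it is considered to have a reasonable possibility" of being related to protocol treatment or study participation, and gives no end date. It adds: "Any secondary malignancy should also be reported in expedited way as an SAE with the appropriate seriousness criteria". Protocol 16.1 defines a secondary malignancy as one caused by treatment for a previous malignancy.

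**Analysis.** SAP 12.1.1 analyses AEs as TEAEs, defined as "AEs occurring or worsening on or after the date of start of treatment and within 30 days after the last treatment administration". For listings it says: "Listings for the corresponding summary tables will be presented separately". For AESIs, SAP 12.1.3 says: "Unless otherwise specified, summaries of treatment-emergent AESIs will be provided for the whole study time and per period, overall and per treatment arm". The follow-up period defined at the start of SAP 12 also ends 30 days after the last dose of either drug. For deaths, SAP 12.1.2 says: "All deaths, as well as deaths within 30 days after last dose of study treatment, will be tabulated".

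**Reports.** SAP 3 lists all of section 12 for both the primary report and the long-term follow-up report. SAP 2 says that the later report will bring more mature data for all endpoints.

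**The concern.** The protocol asks investigators to send in a specific class of late event: serious and judged related to treatment, or a secondary malignancy. The sponsor will hold these records. The SAP then defines its AE outputs so that such events have no place in them, and carries that definition into the one report that should look furthest ahead.

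Completeness of the safety record is what is at stake. Protocol 5.7.7 expects that radiotherapy can cause late damage. The IDMC recommended closing recruitment after noting severe neurological and neuropsychiatric toxicity (Protocol 1.2.1). If SAP 12.1 is followed as written, the long-term report's AE section would not say whether any related serious event was reported after day 30. Estimation and testing of OS and PFS are unaffected.

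**Working it through.** No sample size, power or alpha figure bears on this point, and the plan states no figure to reproduce. The check sets each AE output in the SAP against the collection rule.

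| Output | Where | Reaches past day 30? |
|---|---|---|
| Baseline AEs | SAP 9.1 | No; pre-treatment only |
| Overall TEAE summary, including SAE and related-SAE rows | SAP 12.1.1 | No; treatment-emergent |
| TEAEs by SOC and PT, including SAEs, related SAEs and fatal events | SAP 12.1.1 | No; treatment-emergent |
| Listings | SAP 12.1.1 | No; they correspond to the tables |
| AESI summaries | SAP 12.1.3 | No; treatment-emergent |
| Deaths | SAP 12.1.2 | Yes, but a table of deaths, not of AE terms |

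1. Protocol 16.6 collects related SAEs from day 31 without limit. Secondary malignancies are treatment-caused by definition, so they belong to the same late stream.
2. Every row that reports AE terms stops at or before day 30. Summaries for the whole study time do not help, because the SAP's own follow-up period stops at the same point.
3. One clause of SAP 12.1.1 counts as TEAEs those baseline AEs that resolve and then recur, without restating the window. It does not reach new late SAEs or secondary malignancies.
4. A non-fatal late related SAE therefore appears in none of these outputs. A fatal one is counted as a death, but its AE term is not tabulated.

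For orientation only, here is when the window closes, in days from the start of treatment. It assumes on-schedule completion: 6 weeks of radiotherapy, a 4-week break and maintenance from day 42 + 28 + 1 = 71.

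- Six TMZ cycles, last dose on cycle day 5: 71 + 5 × 28 + 4 + 30 = day 245.
- Eighteen MRZ cycles, last dose on cycle day 15: 71 + 17 × 28 + 14 + 30 = day 591.

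Earlier stopping closes the window earlier. These dates show where the tables stop. They say nothing about how many events lie beyond, and the different closing times are one more reason not to compare late counts between arms.

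**The case against.** The strongest reply is that a 30-day window is what the protocol itself uses. Protocol 8.2.3.2 says safety is followed to 30 days after the last administration, and Protocol 7.2.1 has a similar limit for AE follow-up. The SAP tables are labelled treatment-emergent, so their scope is visible. Late related SAEs still go through expedited reporting and into the six-monthly summary for investigators (Protocol 16.7). All of this stands, and the window itself is not at fault. But a label only tells readers that later events are outside the table, not whether there were any. The six-monthly summary is not specified as a by-arm output, nor is the promise in Protocol 12.1.2 to summarise all collected data.

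A reader might make three stronger inferences that the documents do not support.

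- **That the SAP narrows the protocol's safety analysis.** The SAE tables in Protocol 8.2.3.2 are built "After reconciliation with the SAEs listing extracted from the EORTC pharmacovigilance database" and are not called treatment-emergent, and SAP 12.1 does not repeat that step. Yet those tables sit in a section that opens with the same 30-day sentence, so their reach is ambiguous. The SAP's silence on reconciliation, which its list of main changes does not mention, is not evidence that the step was withdrawn.
- **That late deaths would be tabulated with no cause.** SAP 12.1.2 does not exclude cause. Protocol 7.2.4 requires toxic deaths to be reported as toxicity, and SAP 6.1 provides for frequency tables of all categorical CRF variables. Cause of death may well be shown.
- **That the gap can be sized by the deaths still to come, or by the survival follow-up beyond the window.** Neither measures late related events. Those deaths are from all causes and may include some inside the window. Survival follow-up is not AE observation, because Protocol 6.3.2 schedules no AE assessment in post-treatment follow-up.

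It is also fair to say that the added output would be imperfect. Late reports are spontaneous and may be incomplete, and inclusion depends on a relatedness judgement made with the arm known. That limits how the output may be used, but does not justify leaving it out.

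**Conclusion.** The point holds as a gap between what Protocol 16.6 collects and what SAP 12.1 reports, in both the primary and the long-term follow-up reports. It matters most in the long-term report. It is not a clear departure of the SAP from the protocol, because both state the 30-day safety window.

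The size cannot be given: the documents contain no count or rate of late related SAEs or secondary malignancies, and the number could be zero. No efficacy conclusion changes. This is a worthwhile, inexpensive improvement rather than a serious flaw. The conclusion rests on SAP 12.1 being followed as written, and on no separate by-arm output of these events being planned; none is specified in the two documents.

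**What to change.** Leave the treatment-emergent tables as they are. Add to SAP 12.1, for the long-term follow-up report and for the primary report if any such events exist:

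- One descriptive listing with counts by arm of related SAEs and secondary malignancies with onset or worsening more than 30 days after last dose, taken from the reconciled pharmacovigilance listing.
- SOC and PT, worst grade and time since last dose for each event, with an explicit statement if there are none.
- A footnote that these events are spontaneously reported, selected by open-label investigator attribution, and not to be tested between arms.

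As an optional clarification, show cause of death (toxicity or other) in the SAP 12.1.2 table.

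The cost is a few lines of SAP wording and one listing with counts, from data already collected. The downside is that counts may be low and may be biased between arms, so they can only be read descriptively.

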## 7.2 Evaluation of safety

### 7.2.1 Adverse events

All adverse events will be recorded; the investigator will assess whether those events are treatment-related (reasonable possibility, no reasonable possibility) and this assessment will be recorded in the database for all adverse events. A change in grading will be collected by giving an outcome date to the initial AE. A new adverse event needs to be reported to reflect the change in severity.

The collection period will start at baseline i.e. as from 2 weeks before randomization.

All adverse events will be followed until resolution while the patient remains on study treatment. When the patient discontinues study treatment, suspected adverse reactions (AEs for which there is a reasonable possibility that the treatment caused the AE) that started while on study treatment should be followed for 30 days from the date of the last dose of study treatment or until considered chronic/ stable (as judged by the Investigator), whichever comes first.

New SAEs and serious suspected adverse reactions that occur during the 30-day period from the date of the last dose of study treatment administered should be reported and followed until resolved or considered stable / chronic (as judged by the Investigator).

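### SAP 12.1.1 does not link adverse event records split by a grade change, so a baseline event that only improves on treatment can be counted as treatment-emergent

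*SAP*

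**What the plan says.** Protocol 7.2.1 sets how events are recorded. Collection begins before treatment: "The collection period will start at baseline i.e. as from 2 weeks before randomization". Baseline events are therefore in the same data as later ones. For a change of grade, the protocol says "A change in grading will be collected by giving an outcome date to the initial AE" and then "A new adverse event needs to be reported to reflect the change in severity". It does not distinguish a rise in grade from a fall.

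SAP 12.1.1 defines TEAEs in three steps:

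- The main definition covers "AEs occurring or worsening on or after the date of start of treatment and within 30 days after the last treatment administration".
- Baseline events are added by this rule: "AEs present at baseline which resolve during treatment and occurred again (at any grade) are considered TEAEs".
- Two groups are excluded: "AEs present at baseline which did not resolve within 30 days of the last treatment", and those that resolved and did not come back.

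On counting, "Subjects with multiple occurrences of the same event will be counted only once per subject for each summary". In severity summaries, "the highest grade out of the same TEAEs underwent by a subject will be reported". SAP 12.1.3 applies the treatment-emergent basis to the events of special interest: ataxia with falls, gait and balance problems; dysarthria; and hallucination or delirium.

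The SAP leaves three things open. It does not say whether an AE is one eCRF record or one clinical event. It does not say whether an outcome date entered for a grade change counts as resolution. It does not say how consecutive records of one event are joined.

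**The concern.** Take a patient with a grade 3 gait disturbance at baseline that falls to grade 1 in week 3 and stays there. Under Protocol 7.2.1 this is two records: a baseline record with an outcome date, and a new grade 1 record that starts on treatment. The second record meets the main TEAE definition because its start date is on treatment. The pair can also look like resolution followed by recurrence, and for recurrences the SAP accepts any grade, so no comparison with baseline would catch it. An improvement would then be tabulated as a new event.

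At stake are the any-grade TEAE and special-interest tables, including the table of events seen in more than 10% of subjects in any group. Gait, balance and speech problems are special-interest categories that can also be present at entry in patients with a brain tumour. Section 12 of the SAP feeds both the primary and the long-term follow-up reports.

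**Working it through.** The documents state no figure on this point, so there is none to reproduce. The check has two parts.

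**1. Four event histories under two readings of SAP 12.1.1**

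Record level: any record that starts on treatment is a TEAE. Event level: records are linked, and the event counts if it worsens or recurs after a real gap. The last column reads the exclusion sentence literally.

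| History | Record level | Event level | Exclusion sentence, read literally |
|---|---|---|---|
| A. Baseline grade 2, falls to grade 1, never resolves | TEAE | not a TEAE | excluded |
| B. Baseline grade 1, rises to grade 3, never resolves | TEAE | TEAE | excluded |
| C. Baseline grade 2, resolves, recurs at grade 1 after a gap | TEAE | TEAE | not excluded |
| D. Baseline grade 2, unchanged | not a TEAE | not a TEAE | excluded |

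The two readings differ only on A, the improving event. History B shows a second problem: the main definition includes it as worsening, but the exclusion sentence removes it because it never resolved.

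**2. Size under stated assumptions**

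Inputs, all assumed because the documents give neither baseline prevalence nor improvement rates:

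- p is the genuine TEAE proportion: 30% marizomib, 15% control.
- b is the share of patients without a genuine TEAE who are added because a baseline event improved: 5% to 15%.

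Observed proportion = p + (1 − p)b = 1 − (1 − p)(1 − b). With equal b, observed risk difference = (1 − b) × true risk difference.

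| b (both arms) | Marizomib | Control | Ratio | Difference (points) |
|---|---|---|---|---|
| 0 | 30.0% | 15.0% | 2.00 | 15.0 |
| 5% | 1 − 0.70 × 0.95 = 33.5% | 1 − 0.85 × 0.95 = 19.25% | 1.74 | 14.25 |
| 10% | 1 − 0.70 × 0.90 = 37.0% | 1 − 0.85 × 0.90 = 23.5% | 1.57 | 13.5 |
| 15% | 1 − 0.70 × 0.85 = 40.5% | 1 − 0.85 × 0.85 = 27.75% | 1.46 | 12.75 |

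Unequal b: the observed difference is (p_M − p_C) + (1 − p_M)b_M − (1 − p_C)b_C. It exceeds the true difference once b_M/b_C > (1 − p_C)/(1 − p_M) = 0.85/0.70 = 1.21. For example, with b of 8% in the marizomib arm and 4% in control:

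- Marizomib: 0.30 + 0.70 × 0.08 = 35.6%.
- Control: 0.15 + 0.85 × 0.04 = 18.4%.
- The difference is 17.2 points, above the true 15.0. The ratio is 1.93, slightly below 2.0.

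Unequal b is plausible. Protocol 5.3 allows up to 18 maintenance cycles with marizomib, against 6 in control (up to 12 tolerated), so there is more on-treatment time in which a record can be split.

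Grade 3/4 tables: an improvement adds a false count only when baseline grade 4 falls to grade 3. With an assumed true 20% versus 5% and b of 0.2% to 0.5%, the difference moves from 15.0 to 14.97–14.93 points. Fatal-event tables cannot be affected by an improvement.

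**The case against.** The strongest reply is that the SAP text, read as clinical events, does not make this error. The added rule needs both resolution and recurrence, and a fall from grade 3 to grade 1 is neither. The exclusion sentence removes unresolved baseline events, which covers the gait example. The word *worsening* would be redundant if every grade-change record already counted as a new occurrence, so the wording fits an event-level definition. Protocol 7.2.1 speaks of an outcome date, not of resolution. The CRF completion guidelines, which are not in the documents, may settle how records are linked. Baseline AE grades are tabulated (SAP 9.1) and listings accompany the tables, so a misclassified event could be traced.

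Much of this stands: the SAP does not state a rule that improvements are TEAEs. It does not remove the point, because the protocol itself calls the second record a new adverse event, and no SAP text tells the programmer to rejoin it. The exclusion sentence is also not a dependable safeguard, since applied literally it drops history B.

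A reader might also infer that the rule hides part of the marizomib difference, or that it weakened the safety contrast on which the IDMC acted. The documents support neither. The direction of bias depends on unknown improvement rates and on unequal exposure. The IDMC cited severe neurological and neuropsychiatric disorders and treatment-related grade 3-4 effects, together with no evidence of a survival benefit, and grade 3/4 tables are nearly immune to this problem. Nor do the documents show that early postoperative deficits often improve in this population: eligibility requires recovery from the effects of surgery.

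**Conclusion.** The point holds as a gap in specification. The collection rule splits records at every grade change, and the TEAE definition does not say how to rejoin them. Two competent programmers could produce different any-grade TEAE and special-interest tables from the same data. Under the record-level reading, absolute rates are overstated in both arms.

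The figures above illustrate the size and do not estimate it. They rest on assumed true rates and an assumed b. The direction of bias in the risk difference is not established: it shrinks by the factor (1 − b) if b is equal, and can grow if b is higher with marizomib. Tables of drug-related events would be affected only if the investigator judged the improved event to be related. Serious-event tables depend on how seriousness is carried to the new record, which the documents do not say.

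The conflict between the exclusion sentence and *worsening* does not depend on any assumed rate and needs correction in either case.

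**What to change.** Amend SAP 12.1.1 as follows:

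1. Link consecutive records of the same preferred term that were opened for a grade change into one event before TEAE status is derived.
2. State that an outcome date entered for a grade change is not resolution.
3. Count an event with onset before first dose as a TEAE only if an on-treatment grade exceeds the last pre-dose grade, or if it recurs after documented resolution.
4. Reword the exclusion sentence so that a baseline event that worsens on treatment stays in, whether or not it later resolves.

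The cost is a few lines of SAP text and one derivation step. Grades, dates and outcomes are already collected, so no new data are needed. If tables have already been produced, rerunning the any-grade TEAE and special-interest tables under the linked definition would show whether the choice mattered.
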